### 3 STUDY OBJECTIVES

### 3.1 Objective

The objective of this study is:

- To evaluate the safety and tolerability of a 16-week course of mavacamten in individuals with symptomatic nHCM

## 4 OVERALL STUDY DESIGN AND PLAN

This is a Phase 2, multicenter, exploratory, randomized, double-blind study to evaluate the safety, tolerability, preliminary efficacy, PD, and PK of 2 target drug concentrations of mavacamten compared with placebo in participants with symptomatic nHCM.

Approximately 60 participants with symptomatic nHCM will be enrolled. Participants will be randomized in a 1:1:1 ratio to 1 of 2 active treatment groups or matching placebo group (Figure 1). Randomization will be stratified according to current treatment with beta blocker (yes or no) and type of exercise testing (treadmill or bicycle). Participants will be treated for 16 weeks and then followed up approximately 8 weeks after the last dose of study drug. At Week 6, all participants will undergo blinded dose adjustment based on Week 4 assessments (see Section 2.2 for details). Participants who are treated for their HCM condition (eg, beta blocker or calcium channel blocker) should receive a stable dose of such treatment for at least 2 weeks prior to Screening, and every effort should be made to keep such treatment unchanged (ie, at the same dose) throughout the entire study duration until the EOS visit at Week 24.

During the Screening process, participants will undergo a variety of general, cardiopulmonary, laboratory, [REDACTED], patient-reported outcomes (PRO), and symptom assessments as detailed in Table 1. Participants will receive their first dose of study drug on Day 1. Participants will then undergo a variety of assessments as noted in Table 1 every 2 weeks through Week 16. Assessments will be conducted at the clinical site at Weeks 4, 6, 8, 12, and 16; assessments will be conducted via telephone call at Weeks 2, 10, and 14. At Week 24, participants will undergo EOS procedures as described in Table 1.

[REDACTED]

Data from these PRO assessments will not be made available to the investigators and other site personnel throughout the study. Participants will first be informed of this when they fill out the consent form that is required in order to participate in the trial. The form will include information explaining that the PRO information gathered via the device is not shared with their healthcare provider and they should therefore report any concerning symptoms directly to their physician. Participants will then be reminded of this every time they go to complete the assessment on their handheld device. When the participant logs onto his/her handheld device to complete the assessments, a message screen will be shown advising the participant to consult his/her healthcare provider if he/she has any concerning symptoms. The participant will not be able to continue with the PRO assessments until he/she has acknowledged that he/she has read a provided message that any symptoms, health issues, or other concerns he/she is having may need to be discussed with his/her healthcare team.

[REDACTED]

#### **4.1 Study Duration**

The expected study duration is approximately 28 weeks: up to 4 weeks for Screening and 24 weeks ( $\pm$  7 days) for study conduct, including the 8-week posttreatment follow-up period.

#### **4.2 Independent Data Monitoring Committee**

An Independent Data Monitoring Committee (IDMC) will meet at regular intervals to review study data. The role of the IDMC will be to act in an advisory capacity to the Sponsor with respect to safeguarding the interest of study participants, assessing interim safety data, and advising the Sponsor and investigators on important emerging study conduct issues. The IDMC may formulate recommendations in relation to the evaluation procedures and methodologies being employed to survey and detect potential safety signals. Meeting frequency and membership is described in the IDMC Charter.

## 5 SELECTION AND WITHDRAWAL OF STUDY POPULATION

### 5.1 General Study Population and Clinical Sites

Approximately 60 participants with symptomatic nHCM are expected to enroll in this study at up to 35 clinical sites in the US.

### 5.2 Inclusion Criteria

Each participant must meet the following criteria to be enrolled in this study.

1. Able to understand and comply with the study procedures, including cardiopulmonary exercise testing (CPET), understand the risks involved in the study, and provide written informed consent according to federal, local, and institutional guidelines before the first study-specific procedure
2. Is at least 18 years old at Screening
3. Body weight is greater than 45 kg at Screening
4. Diagnosed with nHCM (hypertrophied and non-dilated left ventricle in absence of systemic or other known cause) consistent with current American College of Cardiology Foundation/American Heart Association and European Society of Cardiology guidelines, ie, the participant must meet at least 1 of the 2 following criteria at the time of Screening:
  - LV wall thickness  $\geq$  15 mm, or
  - LV wall thickness  $\geq$  13 mm with a positive family history of HCM
5. Has documented LVEF  $\geq$  55% at the Screening visit as determined by the echocardiography central laboratory
6. Has adequate acoustic windows to enable accurate transthoracic echocardiograms (TTEs)
7. LVOT peak gradient at rest AND during Valsalva AND post-exercise  $<$  30 mmHg as determined by the echocardiography central laboratory
8. If intracavitary gradient is present and distinctly measurable from the LVOT gradient, then maximal intracavitary gradient at rest AND during Valsalva AND post-exercise  $<$  30 mmHg as determined by the echocardiography central laboratory
9. Has NYHA Class II or III symptoms at Screening
10. Has an elevated NT-proBNP at rest ( $>$  300 pg/mL) at Screening
11. Has safety laboratory parameters (chemistry, hematology, coagulation, and urinalysis) within normal limits (according to the central laboratory reference range) at Screening; however, a participant with safety laboratory parameters outside normal limits may be included if he or she meets all of the following criteria:
  - The safety laboratory parameter outside normal limits is considered by the investigator to be clinically unimportant
  - If there is an alanine aminotransferase or aspartate aminotransferase result, the value must be  $<$  3  $\times$  the upper limit of the laboratory reference range
  - The body size-adjusted estimated glomerular filtration rate is  $\geq$  30 mL/min/1.73 m^2

12. Female participants must not be pregnant or lactating and, if sexually active, must be using one of the following acceptable birth control methods from the Screening visit through 3 months after the last dose of study drug. Hormonal contraceptives are not considered highly effective contraception for this study because it is unknown if mavacamten reduces the effectiveness of hormonal contraceptives.
  - Double-barrier method (eg, male using a condom and female using a diaphragm or cervical cap)
  - Barrier plus nonhormonal contraception (eg, male using a condom and female using a nonhormonal intrauterine device [IUD] or nonhormonal intrauterine system [IUS])
  - Female is surgically sterile for 6 months or postmenopausal for 2 years. Permanent sterilization includes hysterectomy, bilateral oophorectomy, bilateral salpingectomy, and/or documented bilateral tubal occlusion at least 6 months prior to Screening. Females are considered postmenopausal if they have had amenorrhea for at least 2 years or more following cessation of all exogenous hormonal treatments and follicle-stimulating hormone levels are in the postmenopausal range
13. Male participants with sexual partners must agree to use condoms for the duration of the study and for 3 months after the last dose of study medication in order to prevent passing mavacamten to the partner in the ejaculate

### **5.3                   Exclusion Criteria**

A participant who meets any of the following criteria will be excluded from the study.

1. Previously participated in a clinical study with mavacamten
2. Hypersensitivity to mavacamten or any of the components of the mavacamten formulation
3. Participated in a clinical trial where the participant received any investigational drug (or is currently using an investigational device) within 30 days prior to Screening or 5 times the respective elimination half-life (whichever is longer)
4. Has a known infiltrative or storage disorder causing cardiac hypertrophy that mimics nHCM, such as Fabry disease, amyloidosis, or Noonan syndrome with LV hypertrophy
5. Has any medical condition that precludes upright exercise stress testing
6. Has a history of syncope or a history of sustained ventricular tachyarrhythmia with exercise within the past 6 months
7. Has a history of resuscitated sudden cardiac arrest at any time or known appropriate implantable cardioverter defibrillator (ICD) discharge within 6 months prior to Screening
8. Has paroxysmal, intermittent atrial fibrillation with atrial fibrillation present per the investigator's evaluation of the participant's electrocardiogram (ECG) at the time of Screening
9. Has persistent or permanent atrial fibrillation not on anticoagulation for at least 4 weeks prior to Screening and/or is not adequately rate-controlled within 6 months prior to

Screening (note: patients with persistent or permanent atrial fibrillation who are anticoagulated and adequately rate-controlled are allowed)

10. Is currently treated with disopyramide or ranolazine (within 14 days prior to Screening) or treatment with disopyramide or ranolazine is planned during the study
11. For participants on beta blocker, verapamil, or diltiazem, any dose adjustment < 14 days before Screening (see [Section 7.7.2](#))
12. Currently treated or planned treatment during the study with a combination of beta blocker and verapamil or a combination of beta blocker and diltiazem
13. Has been treated with invasive septal reduction (surgical myectomy or percutaneous alcohol septal ablation) within 6 months prior to Screening (note: if a participant has had prior septal reduction therapy, the diagnostic wall thickness criteria and all other eligibility criteria must be met at time of Screening)
14. Documented history of resting or post-exercise LVOT or intracavity gradient > 30 mmHg unless subsequently treated by septal reduction therapy
15. QTcF > 480 ms or any other ECG abnormality considered by the investigator to pose a risk to participant safety (eg, second-degree atrioventricular block type II)
16. Has documented obstructive coronary artery disease (> 70% stenosis in one or more epicardial coronary arteries) or myocardial infarction within the past 6 months
17. Has known moderate or severe (as per the investigator's judgment) aortic valve stenosis at Screening
18. Has any acute or serious comorbid condition (eg, major infection or hematologic, renal, metabolic, gastrointestinal, or endocrine dysfunction) that, in the judgment of the investigator, could lead to premature termination of study participation or interfere with the measurement or interpretation of the efficacy and safety assessments in the study
19. Has pulmonary disease that limits exercise capacity or systemic arterial oxygen saturation
20. Positive serologic test at Screening for infection with human immunodeficiency virus, hepatitis C virus, or hepatitis B virus
21. History of clinically significant malignant disease within 10 years of Screening:
  - Participants who have been successfully treated for nonmetastatic cutaneous squamous cell or basal cell carcinoma or have been adequately treated for cervical carcinoma in situ can be included in the study
  - Participants with other malignancies who are cancer-free for more than 10 years before Screening can be included in the study
22. History or evidence of any other clinically significant disorder, condition, or disease (with the exception of those outlined above) that, in the opinion of the investigator or the medical monitor, would pose a risk to participant safety or interfere with the study evaluation, procedures, or completion
23. Currently taking, or has taken within 14 days prior to Screening, a CYP 2C19 inhibitor (eg, omeprazole), a strong CYP 3A4 inhibitor, or St. John's Wort (see [APPENDIX 2](#) for more details)
24. Prior treatment with cardiotoxic agents such as doxorubicin or similar (see [APPENDIX 2](#))

25. Unable to comply with the study requirements, including the number of required visits to the clinical site
26. Employed by, or a relative of someone employed by MyoKardia, the investigator, or his/her staff or family

#### **5.4 Screening and Enrollment**

An informed consent form (ICF) must be signed and dated by the participant before any study-specific tests or procedures may be performed.

Each participant will be assigned a unique identification number when informed consent has been obtained. The identification number will be assigned based on information obtained from an interactive response system (IXRS). Participants will be considered enrolled once an identification number has been assigned. The identification number will be used to identify the participant throughout the study and should appear on all study-related documentation. Numbers will not include identifiable information. The investigator will ensure that informed consent is obtained from each participant before any study-specific procedures are performed.

Participants that fail to meet all inclusion criteria or present with an exclusion criterion may be re-screened. Refer to the Study Reference Manual for re-screening criteria and procedures.

## **6 RANDOMIZATION AND BLINDING PROCEDURES**

### **6.1 Randomization**

Participants who meet the inclusion/exclusion criteria will be randomized via an IXRS to 1 of 3 groups in a 1:1:1 ratio: 2 active treatment groups and 1 matching placebo group.

Randomization will be stratified according to current treatment with beta blocker (yes or no) and type of exercise testing (treadmill or bicycle).

### **6.2 Study Blinding**

Participants will be randomized to 1 of 3 groups via the IXRS. All participants receive either 5 mg mavacamten or matching placebo from Day 1 to Week 6. Blinded dose adjustment (2.5, 5, 10, or 15 mg mavacamten or placebo) via the IXRS will begin at Week 6 based on PK measurements at Week 4. Study drug administration will occur in a double-blind manner via the IXRS such that the investigator, site staff, the pharmacist, and the participant will not know which study drug is being administered.

In addition, the Sponsor, the central and core laboratories, and clinical site monitors will be blinded to assigned treatment. Echocardiography results (eg, LVEF) performed at clinic visits will be blinded to the investigator and study staff. The 4 different doses of mavacamten and matching placebo will be identical in appearance in order to preserve the blind. Study drug (2.5, 5, 10, or 15 mg mavacamten or matching placebo) will be labeled with a unique identifying number that will be assigned to a participant through the IXRS.

The pharmacovigilance team will be unblinded for suspected unexpected serious adverse reaction (SUSAR) reporting. The IDMC may also review unblinded safety and efficacy data.

### **6.3 Methods for Unblinding**

Unblinding by the investigator independently of the Sponsor also may occur if an AE or toxicity necessitates identification of the medication for the welfare of the participant. Please refer to the IXRS Manual for the unblinding process and contact information.

## 7 STUDY TREATMENT

Study drug is defined as mavacamten or placebo.

All randomized study participants will receive either mavacamten (5 mg from Day 1 to Week 6 and one of a range of doses [2.5, 5, 10, or 15 mg] from Week 6 to Week 16) or matching placebo (Day 1 to Week 16) in a double-blind manner.

### 7.1 Formulation, Packaging, and Labeling of Study Drug

Mavacamten capsules and matching placebo have the same appearance. The study drug presentation is size 2, blue opaque capsules printed with a yellow band on the body and black band on the cap. Each capsule contains white to off-white powder. The active capsules are supplied in 4 strengths: 2.5, 5, 10, and 15 mg.

Mavacamten active and placebo capsules have been manufactured according to current Good Manufacturing Practice (cGMP) regulations. They will be supplied in high-density polyethylene bottles with induction seals and child resistant caps at 30 count per bottle. All study drug will be labeled according to applicable local regulatory guidelines.

The mavacamten active and placebo capsules must be stored at 2°C to 25°C (36°F to 77°F) in the packaging supplied by MyoKardia. Study medication at the investigational site will be stored in a secure area with access limited to authorized study personnel.

### 7.2 Administration and Schedule of Study Drug

Study drug will be supplied to participants via the IXRS in 30-count high-density polyethylene bottles that are appropriately labeled. The participants will be instructed to store their supply of study drug capsules and bottles in a cool, dry place.

Participants will take study drug as directed by the physician. Participants should be instructed to take the study drug under fasting conditions ( $\geq 8$  hours) at approximately the same time every day ( $\pm 4$  hours). Study drug should be taken with approximately 8 ounces of water. If the dosing window is missed, the participant should not take study drug that day. Participants should never take 2 doses of study drug within an 8-hour period.

### 7.3 Treatment Compliance

Compliance with study drug will be monitored by capsule count at Weeks 4, 6, 8, 12, and 16 ([Table 1](#)). Refer to the Pharmacy Manual for details.

### 7.4 Hepatotoxicity Stopping and Rechallenge Rules

Participants with abnormal hepatic laboratory values (eg, alkaline phosphatase [ALP], aspartate aminotransferase [AST], alanine aminotransferase [ALT], total bilirubin [TBL], or international normalized ratio) or signs/symptoms of hepatitis may meet the criteria for withholding of study medication or other protocol-required therapies. Withholding is either

permanent or conditional depending on the clinical circumstances discussed below (as specified in the [US FDA Guidance for Industry: Drug-Induced Liver Injury: Premarketing Clinical Evaluation, July 2009](#)).

#### **7.4.1        *Criteria for Permanent Withholding of Study Drug Due to Potential Hepatotoxicity***

Study drug should be discontinued permanently and the participant should be followed according to the recommendations in [APPENDIX 3](#) for possible drug-induced liver injury (DILI) if all the criteria below are met:

- TBL  $> 2 \times$  upper limit of normal (ULN) or international normalized ratio  $> 1.5$
- AND increased AST or ALT if the baseline value was  $<$  ULN and AST or ALT elevation is  $> 3 \times$  ULN
- AND no other cause for the combination of laboratory abnormalities is immediately apparent. Important potential causes for abnormal AST/ALT or TBL values include, but are not limited to, the following:
  - Obstructive gallbladder or bile duct disease
  - Viral or alcoholic hepatitis (eg, hepatitis A/B/C/D/E, Epstein-Barr virus, cytomegalovirus, herpes simplex virus, varicella)
  - Hypoxic or ischemic hepatopathy or congestive hepatopathy in association with significant right-sided heart failure
  - Concomitant administration of other hepatotoxins, including drugs that inhibit bilirubin glucuronidation (eg, indinavir, atazanavir, irinotecan) or herbal or dietary supplements
  - Heritable disorders causing impaired glucuronidation (eg, Gilbert syndrome);  $\alpha$ -1 antitrypsin deficiency
  - Autoimmune hepatitis
  - Nonalcoholic steatohepatitis or other fatty liver disease

If an alternative cause for hepatotoxicity is identified or less stringent conditions developed than what is noted above, the investigator will determine whether study drug and other protocol-required therapies should be permanently or temporarily discontinued based on participant population and/or severity of the hepatotoxicity or event, as deemed appropriate for the safety of the participant.

#### **7.4.2        *Criteria for Conditional Withholding of Study Drug Due to Potential Hepatotoxicity***

For participants who do not meet the criteria for permanent withholding of study medication outlined above, study drug should be withheld if ANY of the following criteria are met, and the participant should be evaluated for DILI:

- Elevation of either AST or ALT, regardless of baseline AST or ALT value, if:
  - $> 8 \times \text{ULN}$  at any time
  - $> 5 \times \text{ULN}$  and  $< 8 \times \text{ULN}$  for  $\geq 2$  weeks
  - $> 5 \times \text{ULN}$  and  $< 8 \times \text{ULN}$  and unable to adhere to enhanced monitoring schedule
- OR: clinical signs or symptoms that are, in the opinion of the investigator, consistent with hepatitis (such as right upper quadrant pain/tenderness, fever, nausea, vomiting, jaundice, rash or eosinophilia  $> 5\%$ ). If such signs or symptoms are coupled with ALT or AST elevations  $> 3 \times \text{ULN}$ , study medication should be withheld
- OR: TBL  $> 3 \times \text{ULN}$  at any time
- OR: ALP  $> 8 \times \text{ULN}$  at any time

Study drug should be withheld pending an investigation into alternative causes of DILI. If study medication is withheld, the participant should be followed according to recommendations in [APPENDIX 3](#) for possible DILI. Rechallenge may be considered if an alternative cause, such as acute hepatitis B infection, is discovered and the laboratory abnormalities resolve to normal or baseline ([Section 7.4.3](#)).

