#### **7.4.3        *Criteria for Rechallenge of Study Drug After Potential Hepatotoxicity***

The decision to rechallenge the participant should be discussed and unanimously agreed by the investigator, IDMC, and Sponsor.

If signs or symptoms recur with rechallenge, then study drug will be permanently discontinued. Participants who clearly meet the criteria for permanent discontinuation (as described in [Section 7.4.1](#)) should never be rechallenged.

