**10.1 Treatment Discontinuation*****10.1.1 Temporary Treatment Discontinuation***

Temporary treatment discontinuation may be considered by the investigator in the case of an AE/SAE or for another reason.

As a general rule, any discontinuation of study drug should be initially considered temporary unless permanent treatment discontinuation is mandated by the protocol (see [Section 10.1.3](#)).

In the case of discontinuation for an AE/SAE, the investigator should make a best effort to resume study drug as soon as practically possible, assuming there are no safety concerns (ie, the investigator is satisfied that in his or her medical judgment, the study drug is unlikely to be responsible for the event concerned).

All temporary treatment interruptions should be recorded in the eCRF.

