***10.1.2 Permanent Treatment Discontinuation***

After a temporary treatment discontinuation, if a safety concern has not resolved or stabilized or the investigator suspects that study drug is responsible, the investigator may consider a treatment discontinuation as permanent. The investigator should make a best effort to contact the monitoring team before considering any treatment discontinuation as permanent.

Permanent treatment discontinuation should be considered a last resort. Every effort should be made to collect important safety data if feasible and the study participant agrees.

In all cases, participants should be encouraged to discuss stopping study drug with the investigator or the investigator's designee so that questions can be addressed, concomitant therapy can be adjusted if needed, and a follow-up assessment be arranged.

Any permanent treatment discontinuation should be recorded in the eCRF.

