***10.1.3 Criteria for Permanent Treatment Discontinuation***

The following reasons will lead to permanent treatment discontinuation:

- Safety threshold being met (see [Section 7.5](#))

- Pregnancy
- New or worsening heart failure associated with systolic dysfunction
- Any breaking of the study blind requested by the investigator
- Continued administration of study drug is considered by the investigator to be detrimental to the participant's safety or well-being
- If all the criteria are met for possible DILI (see [Section 7.4.1](#))
- The participant requests to discontinue study drug
- The Sponsor requests that the participant permanently discontinues study drug

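### After a conditional liver hold, Protocol Sections 7.4.2/7.4.3 and Section 10.1.1 give different rules for restarting study drug, and nothing says which governs

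*Protocol*

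**What the plan says.** **Section 7.4 (liver rules).** Section 7.4.1 defines the permanent stop: all of its criteria must be met. Its closing paragraph covers cases where another cause is identified or the findings fall short of those criteria. There the investigator decides whether the discontinuation is permanent or temporary.

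Section 7.4.2 defines the conditional hold, for example AST or ALT above 8 × ULN at any time. It says "Study drug should be withheld pending an investigation into alternative causes of DILI" and then "Rechallenge may be considered if an alternative cause, such as acute hepatitis B infection, is discovered and the laboratory abnormalities resolve to normal" (or baseline), with a pointer to Section 7.4.3. Section 7.4.3 says "The decision to rechallenge the participant should be discussed and unanimously agreed by the investigator, IDMC, and Sponsor". It excludes rechallenge outright only for one group: "Participants who clearly meet the criteria for permanent discontinuation", meaning Section 7.4.1.

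**Section 10.1 (treatment discontinuation in general).** Under Section 10.1.1 every stop starts as temporary unless the protocol mandates a permanent one, with a reference to Section 10.1.3. After a stop for an AE or SAE, "the investigator should make a best effort to resume study drug as soon as practically possible, assuming there are no safety concerns". The text explains the absence of safety concerns as the investigator's own medical judgment that study drug probably did not cause the event.

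Section 10.1.2 lets the investigator consider a stop permanent "if a safety concern has not resolved or stabilized or the investigator suspects that study drug is responsible", and calls a permanent stop a last resort. Section 10.1.3 lists the mandatory permanent stops. Its liver entry reads "If all the criteria are met for possible DILI" and refers to Section 7.4.1 only.

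**SAP.** Section 3.3 leaves the withholding rules to the protocol.

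**The concern.** A participant on a Section 7.4.2 hold falls under both sets of rules, and they differ on who decides and on what must be true first. Section 10.1.1 also presses towards early resumption. A site that opens Section 10 to manage an interrupted participant finds a complete instruction there and no sign that a stricter liver rule exists elsewhere.

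At stake is re-exposure after a possible drug-induced liver injury without the three-party check in Section 7.4.3, in a trial whose stated objective is safety and tolerability. The protocol allows up to 35 sites for about 60 participants, so few sites will see more than one such case and uniform practice will not develop by itself. Participants with the same liver values could be re-exposed at one site and kept off drug at another.

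**Working it through.** No arithmetic decides this point, so the check is a comparison of the text.

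**Step 1. Does Section 10.1.1 reach a Section 7.4.2 hold?** Yes, on its face.
- Protocol Section 11.1.1 requires test abnormalities that lead to interruption of study medication to be captured as AEs, so a hold for ALT above 8 × ULN is normally a stop for an AE.
- The closing paragraph of Section 7.4.1 itself describes lesser liver findings in terms of temporary or permanent discontinuation.
- The exception in Section 10.1.1 is a permanent stop mandated under Section 10.1.3. That list reaches liver findings by name only through Section 7.4.1, and its safety-threshold entry points to Section 7.5. Section 7.4.2 is not listed.

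**Step 2. Compare the restart rules.**

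| | Section 10.1.1 | Sections 7.4.2 and 7.4.3 |
|---|---|---|
| Who decides | Investigator | Investigator, IDMC and Sponsor, unanimously |
| Cause | Drug judged an unlikely cause | Alternative cause discovered |
| Laboratory values | No condition stated | Back to normal or baseline |
| Direction | Resume promptly | Rechallenge may be considered |

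The closing paragraph of Section 7.4.1 adds to the first row: inside the liver section too, the investigator alone chooses between temporary and permanent. Section 10.1.2 asks for contact with the monitoring team before a stop is made permanent; Section 10.1 names no contact before a restart.

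**Step 3. Look for precedence.** None is stated. Sections 7.5 and 7.5.1 refer forward to Sections 10.1.2, 10.1.3 and 10.1.4. Section 7.4 has no reference to Section 10, and Section 10.1.1 has none to Section 7.4.

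**Step 4. Two hypothetical participants**, both with baseline ALT 0.8 × ULN, a rise to 9 × ULN (above 8, so Section 7.4.2 applies), and Section 7.4.1 not met.
- *Case A:* a viral cause is proven and ALT returns to 0.8 × ULN. The cause and laboratory conditions of Section 7.4.2 are met. Section 10.1.1 asks the investigator to resume. Section 7.4.3 still needs three parties to agree. The only difference is who decides.
- *Case B:* a viral cause is suspected but unproven and ALT has fallen to 2 × ULN, which is above both 1 × ULN and baseline. Section 7.4.2 is not satisfied on cause or values. Under Section 10.1.1 the outcome turns on whether the investigator is satisfied that the drug is unlikely to be responsible; if so, the text asks for resumption.

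**Step 5. A hold with no cause found.** It is temporary by default (10.1.1). The investigator may make it permanent (closing paragraph of 7.4.1; 10.1.2; the 10.1.3 entry on detriment to the participant), and so may the Sponsor (10.1.3). Section 7.4.2 offers no restart. No text says where such a hold ends if nobody acts.

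**Step 6. Effect on the data.**
- Section 10.1.4 asks for an early termination visit only after a permanent stop, so the class of the hold sets when those assessments occur.
- SAP Section 7 counts participants who discontinue treatment, and SAP Section 13.1 tabulates TEAEs leading to permanent discontinuation. Both depend on the class.
- SAP Section 13.3 lists two normalization categories: never, and after permanent discontinuation. Normalization during an open hold fits neither.

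**Step 7. Scale.** The documents give no rate of conditional holds. One participant is 1/20 = 5% of a planned arm and 1/60 = 1.7% of the trial.

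**The case against.** The strongest reply is that Section 7.4 is the specific rule and Section 10.1.1 the general one. A site can satisfy both by treating Sections 7.4.2 and 7.4.3 as extra conditions for liver holds, and a site that restarted on Section 10.1.1 alone would breach Section 7.4.3. This stands in part. A reader might infer that the protocol permits one investigator to re-expose a participant; it does not. But the protocol never says that the specific rule prevails. The general-rule wording in Section 10.1.1 qualifies the temporary default, not the resumption sentence, and the exception it names does not cover Section 7.4.2.

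A second reply is that resumption is conditional on there being no safety concerns, so a careful investigator would not restart in Case B. That is fair for Case B. It does not help in Case A, and Section 10.1.1 defines the condition by the investigator's own judgment.

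Three further inferences are tempting and fail.
- *That no rule classes an unexplained hold.* Sections 7.4.1, 10.1.1, 10.1.2 and 10.1.3 supply a default, decision-makers and routes to a permanent stop. Only the final status is missing.
- *That Section 10.1.2 accepts stabilization as grounds for restart.* Its wording is a trigger for considering a stop permanent; it sets no restart condition.
- *That the early termination assessments would be lost.* Week 16 and early termination share one column in the schedule, so a participant on an open hold who stays in the study is due the same assessments at Week 16. Appendix 3 liver follow-up applies to permanent and conditional withholding alike. The effect is on timing and label.

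**Conclusion.** The point holds as an inconsistency between two stated rules. For a conditional liver hold, Sections 10.1.1 and 7.4.2/7.4.3 differ on decision-maker, cause and laboratory condition, and neither precedence nor a cross-reference resolves the difference. The exposure is a site acting on Section 10.1.1 alone; the protocol does not authorize that. The missing final status of an unexplained hold is a smaller, related gap that affects visit timing and discontinuation counts.

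The likely number of cases is unknown and may be zero. The effect on planned analyses is limited, and the sample size is unaffected. The reason to act is safety: re-exposure after a possible liver injury should not depend on which section a site reads. The conclusion assumes that a Section 7.4.2 hold is a stop for an AE, which Section 11.1.1 supports, and that no redacted text or manual outside these documents sets the precedence.

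**What to change.** Reconcile Sections 7.4.1 (closing paragraph), 7.4.2 and 7.4.3 with Sections 10.1.1 to 10.1.3:

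1. In Section 10.1.1, add one sentence saying which section governs resumption after a hepatic hold, with a cross-reference, and a matching pointer in Section 7.4.2. Align the closing paragraph of Section 7.4.1 with it on who decides.
2. In Section 10.1.2 or 10.1.3, state how a Section 7.4.2 hold with no alternative cause found is finally classed, so that it is clear whether and when the Section 10.1.4 early termination visit applies.
3. Make the SAP discontinuation counts (Sections 7 and 13.1) and the liver normalization categories (Section 13.3) follow that classification.

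The sponsor must choose the clinical rule; this review does not say which is right. The cost is about two protocol sentences plus the pointers, in an amendment or site clarification, and a small SAP edit. No visit, test or participant is added.
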